### 3.2.3. Overall Benefit/Risk Conclusion

The results of previous studies of osivelotor in healthy volunteers and SCD adult participants support the investigation of osivelotor for SCD. There is a favorable benefit-risk profile to support the rationale for this study. Taking into account the measures to minimize risk to participants, the potential risks associated with osivelotor are justified by the anticipated benefits that may be afforded to participants with SCD.

### 3.3. Study Rationale

This is a multicenter, global, open-label extension study to evaluate the long-term safety, tolerability and SCD related complications of participants who have been treated with osivelotor. Gathering more patient-years of exposure to osivelotor will allow the Sponsor to further understand and characterize the safety profile of osivelotor.

All participants in this study are participants with SCD who have previously participated in an osivelotor clinical study. Participation in this study will provide continued access to

treatment until the participant has access to osivelotor from an alternative source (eg, through commercialization, a managed-access program, or a Sponsored initiative) or until the Sponsor decides to terminate the Study. Some participants in this study will have received osivelotor or placebo in a prior study in a blinded fashion and therefore this study will evaluate the first exposure to osivelotor in some participants. As such, the safety of initial exposure to osivelotor will also be evaluated in this study.

The daily maintenance dose for adult participants entering the study will be 150 mg osivelotor, which is the optimal dose selected from Part A of C5351004. The daily maintenance dose for all adult participants who have already enrolled into C5351005 prior to this amendment may be adjusted to the selected dose of 150 mg. Adolescent and pediatric participants from C5351004 Parts B and C will be administered a dose that provides generally equivalent exposure to adult participants.

#### 4. OBJECTIVES, ENDPOINTS, AND ESTIMANDS

The objectives of the study will be assessed by the endpoints and estimands as shown in Table 5.

**Table 5. Objectives, Endpoints and Estimands**

Objectives	Endpoints	Estimands
Primary:	Primary:	Primary:
To evaluate the long-term safety of osivelotor in participants with SCD.	
 
Incidence of TEAEs, changes in laboratory assessments, and changes in vital signs.
 
	The safety estimand for the primary endpoints will consider all safety data collected. Specifically, all data collected on or after obtaining informed consent will be included in the analysis.
Secondary:	Secondary:	Secondary:
To evaluate frequency of SCD-related complications.  To evaluate the effects of long-term use of osivelotor on hemolytic anemia.	
 
Annualized rate of VOC.
 
Incidence of SCD-related SAEs.
 
Change from baseline in hematological laboratory parameters, including hemoglobin, reticulocytes, lactate dehydrogenase, and unconjugated bilirubin.
 
	Not Applicable
Exploratory:	Exploratory:	Exploratory:

**Table 5. Objectives, Endpoints and Estimands**

Objectives	Endpoints	Estimands
To evaluate the long-term effects of osivelotor treatment on inflammation, erythropoietin levels, SCD-specific biomarkers, and HRQOL assessments.	
 
• Change from baseline in adhesion of whole blood to microfluidic channels.
 
• Change from baseline in RBC sickling from peripheral blood smears.
 
• Change from baseline in RBC deformability and RBC mitochondrial content.
 
• Change from baseline in albumin-to-creatinine ratio and kidney injury molecule.
 
• Change from baseline in erythropoietin levels.
 
• Change from baseline in haptoglobin, hemopexin, and soluble C3.
 
• Change from baseline in HRQOL assessments including PROMIS SF Fatigue 13a, PROMIS SF Pain Interference 8a, PROMIS NRS Pain intensity, PGI-C of fatigue and pain, CGI-C of SCD, PGI-S of fatigue and pain, and CGI-S of SCD, EuroQol EQ-5D-5L, and WPAI-CIQ:SCD.
 
	Not Applicable
To evaluate the PK parameters of long-term exposure to osivelotor	
 
• Blood and plasma concentrations of osivelotor.
 
	Not Applicable

Abbreviations: CGI-C, Clinician's Global Impression of Change; CGI-S, Clinician's Global Impression of Severity; PGI-C, Patient's Global Impression of Change; PGI-S, Patient's Global Impression of Severity; PK, pharmacokinetic; PROMIS, Patient-Reported Outcome Measurement Information System; HRQOL, health-related quality of life; RBC, red blood cell; SCD, sickle cell disease; SF, short form, WPAI-CIQ:SCD, Work Productivity and Activity Impairment Questionnaire plus Classroom Impairment Questions: Sickle Cell Disease.

## 5. STUDY DESIGN

### 5.1. Overall Design

This multicenter, global, open-label extension study is designed to assess the safety of long-term treatment with osivelotor in participants with SCD. The study will be conducted globally and will be available to eligible participants enrolled in a prior Pfizer-sponsored osivelotor clinical study (originating study). Participants must meet the entry criteria for this

study to be eligible for enrollment (see Section 6.1). The study will have a global distribution, and up to approximately 500 participants will be enrolled.

Eligible participants will receive osivelotor administered orally daily if they continue to receive clinical benefit that outweighs risk, as determined by the Investigator, until the participant has access to osivelotor from an alternative source (eg, through commercialization or a managed-access program).

Eligible participants will receive open-label osivelotor at Baseline (Day 1). It is intended that Day 1 coincides with the final visit from the originating osivelotor study. End of Treatment (EOT) assessments from the originating study will serve as Baseline assessments for this study. If Day 1 for this study is greater than 7 days from the completion of the originating study, new baseline assessments will be obtained. If during the period between Day 1 of this study and completion of the originating study no dose is received for greater than 3 consecutive days, an appropriate loading dose will be administered prior to continued maintenance dosing (see Section 11.3 for detail). Additional assessments that may not have been included in the prior EOT assessments are outlined in the Schedule of Assessments and will need to be completed prior to study drug administration.

Participants who participated in Part A of C5351004 or any other open label osivelotor study, will undergo safety and outcome assessments at Baseline (Day 1) and every 12 weeks thereafter (Table 2).

Participants from Part B of C5351004, or any other randomized, blinded, placebo controlled osivelotor study will undergo safety and outcome assessments at Baseline (Day 1), Week 8, Week 16, Week 24, and every 12 weeks thereafter (Table 3).

Pediatric participants from Part C of C5351004 will undergo safety and outcome assessments at Baseline (Day 1), Week 2, Week 4, Week 8, Week 12, Week 16, Week 20, Week 24, and every 12 weeks thereafter (Table 4).

Participants will be followed for approximately 12 weeks after completing dosing to further assess safety. Participants should return to the study site for an EOS visit approximately 12 weeks after the last dose of study drug.

## 5.2. Scientific Rationale for Study Design

This study is an open-label study to evaluate the safety of long-term administration of osivelotor without a comparator. Participants in this study will have participated in a controlled clinical trial of osivelotor (originating study) in which they will have received osivelotor or placebo. Given the long half-life of osivelotor at the dose to be evaluated in this study, most of the participants are expected to maintain target concentrations throughout the study.

## 5.3. Justification for Dose

The daily maintenance dose for adults in the open label extension study will be 150 mg, which was the optimal efficacious dose determined from Part A of C5351004. The daily maintenance dose for all adult participants who have already enrolled in C5351005 prior to this amendment may be adjusted to 150 mg.

Adolescent and pediatric participants from C5351004 Parts B and C will be administered a dose that provides generally equivalent exposure to adult participants.

Further modifications to the loading doses may be made based on cumulative data from a population PK (PPK) model. Additionally, if there are safety/tolerability issues or lack of biomarker response at higher doses in the originating study, a drug dose reduction may be instituted as noted in Section 11.3.

The methodology for loading dose selection used in this open label study will differ for participants completing Parts A, B, and C of C5351004 and are shown in Section 11.3 and Table 6. For participants from the parent study who have been off study drug treatment greater than 3 consecutive days prior to enrolling into this study, a new loading dose regimen will be initiated as shown in Section 11.3.

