**Study Arms:**

Study Arms	
Arm Title	Osivelotor (PF-07940367 or GBT021601)
Adults	Adult participants enrolling from C5351004 Part A and Part B will receive 150 mg maintenance dose. Dose adjustment and/or loading dose will be determined based on previous intervention/dose received in C5351004.
Adolescents and Pediatrics	Adolescent and pediatric participants from C5351004 Parts B and C will be administered a dose that provides generally equivalent exposure to adult participants.

**Duration of Treatment:** Participants may receive study drug for up to 252 days, as long as they continue to receive clinical benefit that outweighs risk as determined by the Investigator and/or until the participant has access to osivelotor from an alternative source (eg, through commercialization, a managed-access program, or a Sponsored initiative) or until the Sponsor decides to terminate the study.

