## Clinical Experience

Two Phase 1 clinical studies have been completed.

A first-in-human single ascending and multiple ascending dose (SAD/MAD) study in healthy participants (GBT021601-011) has been completed. Safety and PK data on single doses up to 3000 mg in healthy participants demonstrated that osivelotor was well tolerated with a linear dose-dependent increase in percent Hb occupancy. Absorption following a single oral dose was relatively quick in plasma, with  $T_{max}$  generally ranging 0.5-3 h. Peak concentration in whole blood was achieved slower with  $T_{max}$  generally ranging 8-48 h. The terminal elimination half-life of approximately 25 to 28 days in plasma and blood was observed in healthy volunteers; however, approximately 3-fold lower terminal half-life (approximately 10 days) in plasma and whole blood was observed in SCD patients. PK exposure is generally dose-proportional and displays a high partitioning to whole blood (blood/plasma ratios of ~213 and ~68 for healthy volunteers and SCD patients, respectively, following a single 100 mg dose).

In addition, a Phase 1b Study GBT021601-012 in adult participants with SCD was conducted to evaluate the PK, safety, tolerability, and PD of single dose and MAD of osivelotor. In this open label study, a within participant dose escalation was explored. Safety, tolerability, and available PK data after each dose level were reviewed by the Safety Review Committee before escalation to the next dose level. Six adults with SCD received a single 100 mg dose of osivelotor. After an 8-week washout, participants received osivelotor loading doses of 300 mg on Day 1 and 200 mg on Day 2, followed by a maintenance dose of 50 mg/day for 5 weeks. Dose escalation occurred at Week 13 with participants receiving a 500 mg dose on Day 91, 400 mg dose on Day 92, followed by a maintenance dose of 100 mg/day for approximately 3 weeks. The study was amended to evaluate an additional maintenance dose of 150 mg/day over 6 weeks.

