Preliminary data from these studies demonstrates that osivelotor has an acceptable safety and tolerability profile in healthy volunteers and participants with SCD as further described in Section 3.2. After single doses of osivelotor, blood and plasma PK and the mean % Hb occupancy of osivelotor increased in a linear manner following a single oral dose in healthy volunteers (Study GBT021601-011). In the initial part of the GBT021601-012 study of six SCD participants, after treatment at two dose levels, 50 mg for 5 weeks and 100 mg for 3

weeks, the % Hb occupancy averaged 32.6% (range 19.7% to 41.8%) and Hb levels increased by up to 3.1 g/dL (mean increase of 2.3 g/dL). Within the same timeframe, all participants demonstrated improvements in hematologic parameters, including reticulocytes and absolute reticulocytes, lactate dehydrogenase (LDH), and indirect bilirubin (Brown, Redfern et al. 2021).

GBT021601-013 is an ongoing Phase 1, single-center, open-label study to assess the mass balance, excretion, and PK of a single oral dose of [C]-osivelotor in healthy participants.

GBT021601-014 is an ongoing Phase 1, open-label, single-dose, non-randomized, parallel group study to evaluate the PK, safety, and tolerability of osivelotor in adult participants with renal impairment.

C5351004 is a three-part, multicenter, Phase 2/3 study of orally administered osivelotor in participants with SCD. Part A will evaluate the safety, tolerability, and efficacy of 12 weeks of osivelotor in adult participants with SCD, and determined the optimal dose of 150 mg for Part B. Part B will evaluate the efficacy of 150 mg osivelotor versus placebo in adult and adolescent participants with SCD for 48 weeks. Part C is a single-arm study which will evaluate the PK and safety of single and multiple doses of open-label osivelotor administered to pediatric participants. The study is ongoing.

Participants with SCD who participated in an osivelotor clinical study may be eligible to enroll in this open-label extension study (C5351005).

A detailed description of the chemistry, pharmacology, efficacy, and safety of osivelotor is provided in the PF-07940367 Investigator's Brochure (IB) (Pfizer, 2023), which is the Single Reference Safety Document (SRSD) for this study.

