**Table 6. Doses Planned Based on Participation from C5351004**

Participants from Part	Planned Dose to Initiate Treatment in Open Label Extension	Dose Adjustment
A	150 mg osivelotor	If dose is increased, a loading dose may be required. Details on the loading doses are provided in Section 11.3. The maintenance dose for all participants who have already enrolled in C5351005 prior to this amendment may be modified to 150 mg.
B	Adults: Initiate or continue with QD osivelotor 150 mg dose from Part B of C5351004. Adolescents: Initiate or continue with QD dose of osivelotor from Part B of C5351004.	Adults: Not applicable  Adolescents: Adolescent participants will be administered a dose that provides generally equivalent exposure to adult participants.
C	Continue with QD assigned dose of osivelotor from Part C of C5351004.	Treatment may be modified based on emerging data from C5351004. Adolescent and pediatric participants will be administered a dose that provides generally equivalent exposure to adult participants.

Abbreviations: QD, once daily.

Detailed information on loading dose and maintenance dose to be used based on prior participation in C5351004 can be found in Section 11.3.

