**Table 7. Study Drug Information**

Study Intervention	
Intervention Name	Osivelotor (PF-07940367 or GBT021601)
Type	Drug
Use	Experimental
IMP or NIMP/AxMP	IMP
Dose Formulation	Tablet (or age appropriate oral formulation for pediatric participants <6 years of age)
Unit Dose Strength(s)	100 mg/tablet, 25 mg/tablet
Dosage Level(s)	100 mg, 150 mg, 200 mg
Route of Administration	oral
Sourcing	Provided centrally by the sponsor.
Packaging and Labeling	Study intervention will be provided in bottles. Each bottle will be labeled as required per country requirement. Provided blinded.
SRSD	PF-07940367 Investigator's Brochure
Study Arms	
Arm Title	Osivelotor (PF-07940367 or GBT021601)
Adults	Adult participants enrolling from C5351004 Part A and Part B will receive 150 mg maintenance dose. Dose adjustment and/or loading dose will be determined based on previous intervention/dose received in C5351004. Details are provided in Appendix 1.
Adolescents and Pediatrics	Adolescent and pediatric participants from C5351004 Parts B and C will be administered a dose that provides generally equivalent exposure to adult participants.

See [Appendix 1: Detailed Dosing Information For Osivelotor](#) for dose information for participants rolling into this study.

Osivelotor will be administered orally. Study drug will be dispensed to the participant for completion of loading doses and initiation of maintenance dosing at home daily until the next clinical site visit.

Study drug should be taken two hours before a meal or one hour after a meal. Each dose will be administered orally with approximately 240 mL of water (additional water to complete dosing is allowed). Participants should swallow the tablets ( $\geq 6$  years old) or age appropriate

pediatric formulation (<6 years old) within 5 minutes. If the participant vomits, the dose should not be repeated.

On the days that PK samples are to be taken, study drug is to be taken in the clinic and the participant must record the time and date of the last three doses of study drug taken at home. It is anticipated that these samples are to be taken  $24 \pm 3$  hours after the last dose at home.

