## 11.2. Supporting Documentation

### 11.3. Appendix 1: Detailed Dosing Information For Osivelotor

#### Dose for Participants Enrolling from Part A of C5351004

**Table 13. Dose for Participants Enrolled Directly from Part A of C5351004**

Maintenance Dose in Part A of C5351004	Maintenance Dose in C5351005 a
100 mg QD	Stay at 100 mg QD
	Increase to 150 mg QD
150 mg QD	Stay at 150 mg QD
	Decrease to 100 mg QD
Up to 200 mg QD	Stay at up to 200 mg QD
	Decrease to 150 mg QD
	Decrease to 100 mg QD

Abbreviations: QD, once daily.

a Until the analysis is completed from Part A of C5351004, the original dose from Part A of C5351004 should be continued in C5351005. After the optimal efficacious dose is determined in C5351004, participants may have their dose adjusted to the optimal efficacious dose in C5351005.

If there is a delay in dosing for participants from Part A of the C5351004 study prior to entry into this OLE study, a modified loading dose will be administered depending on the dose received in the previous study as follows:

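### Appendix 1 dosing tables were not aligned with the 150 mg rule for Part A adults entering under Amendment 4: Table 13 still allows them to stay on 100 mg or up to 200 mg, and re-loading is keyed to the previous dose

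*Protocol*

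**What the plan says.** The main text gives one starting dose to adults entering from Part A. Section 5.3 says "The daily maintenance dose for adults in the open label extension study will be 150 mg". The Synopsis and Table 7 say "Adult participants enrolling from C5351004 Part A and Part B will receive 150 mg maintenance dose". Section 3.3 says "The daily maintenance dose for adult participants entering the study will be 150 mg osivelotor", and Table 6 gives 150 mg as the initiating dose for Part A. Section 3.1 reports that Part A "determined the optimal dose of 150 mg for Part B", and Section 5.3 also describes the dose as already determined.

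Adults already in the extension are treated differently. Table 6 says "The maintenance dose for all participants who have already enrolled in C5351005 prior to this amendment may be modified to 150 mg", and Sections 3.3 and 5.3 use the same permissive wording for that group.

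Tables 6 and 7 send sites to Appendix 1 (Section 11.3) for detail. There, Table 13 lists options by Part A dose:
- former 100 mg: remain, or go up to 150 mg;
- former 150 mg: remain, or go down to 100 mg;
- former 200 mg: remain at up to 200 mg, or go down to 150 or 100 mg.

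No row depends on enrolment date. The footnote begins "Until the analysis is completed from Part A of C5351004, the original dose from Part A of C5351004 should be continued in C5351005", then allows adjustment once the dose is known.

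For gaps in dosing, the lead-in to Table 14 makes the re-loading regimen depend on what the participant took in the parent study. The Synopsis and Table 7 agree: "Dose adjustment and/or loading dose will be determined based on previous intervention/dose received in C5351004". The Table 14 columns are headed only by maintenance dose (100, 150, 200 mg), without naming the study.

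**The concern.** These are the instructions a site applies on Day 1. A new Part A entrant could be kept on 100 mg or 200 mg under Table 13 although the main text sets 150 mg. A new entrant who does move to 150 mg after a gap could be loaded from the column for a dose that is no longer being given. Long gaps are foreseen: Table 1 is a schedule for starts delayed by more than 42 days, and SAP Section 2.2.3 defines that group. What is at stake is a maintenance or loading dose that does not match the intended regimen. The protocol's one named theoretical drug risk, decreased oxygen delivery (Section 3.2.1), makes too high a dose the more sensitive direction.

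**Working it through.** **1. Maintenance dose, texts side by side.** For a Part A adult entering under Amendment 4 with no reason for reduction:
- former 100 mg: main text 150 mg; Table 13 permits 100 or 150 mg;
- former 150 mg, staying on that dose: both give 150 mg;
- former 200 mg: main text 150 mg; Table 13 permits up to 200, 150 or 100 mg.

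For an adult enrolled before Amendment 4, the main text makes the change optional, so the stay rows agree with it. The fault is that Table 13 does not separate the two groups.

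**2. Loading totals from Table 14** (mg per day × days):

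| Missed days | 100 mg column | 150 mg column | 200 mg column | 100/150 | 200/150 |
|---|---|---|---|---|---|
| >3 to <7 | 200×3 = 600 | 300×3 = 900 | 300×4 = 1200 | 67% | 133% |
| 7 to <14 | 200×5 = 1000 | 300×5 = 1500 | 300×7 = 2100 | 67% | 140% |
| 14 to <42 | 200×7 = 1400 | 300×7 = 2100 | 300×10 = 3000 | 67% | 143% |
| 42 or more | 200×7 = 1400 | 300×7 = 2100 | 300×14 = 4200 | 67% | 200% |

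For anyone moving from 100 or 200 mg to 150 mg, the two keys differ in every row.

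**3. What this means for drug level (size only).** The input from the protocol is the half-life in Section 3.1: "approximately 3-fold lower terminal half-life (approximately 10 days) in plasma and whole blood was observed in SCD patients". Assumed here: one compartment, equal bioavailability, prior steady state, and 42 days from the last dose to the first loading dose.

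- Daily retention k = 2^(−1/10) = 0.933.
- Steady-state amount just after a dose = dose/(1 − k): 1493, 2240 and 2987 mg for 100, 150 and 200 mg.
- Amount after n loading doses of L mg, no residual = L(1 − k^n)/(1 − k). For 42 or more days: 1148, 1722 and 2782 mg, or 77%, 77% and 93% of each column's own steady state.
- Residual after 42 days = 2^(−4.2) = 5.4%: 81 mg (former 100 mg) and 163 mg (former 200 mg). By the last loading dose it is multiplied by k^(n−1): 0.660 for 7 doses, 0.406 for 14.

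Level at the end of loading, as a share of the 150 mg steady state (2240 mg):
- former 200 mg, 200 mg column: 2782 + 163×0.406 = 2848 mg, 127%;
- former 200 mg, 150 mg column: 1722 + 163×0.660 = 1829 mg, 82%;
- former 100 mg, 100 mg column: 1148 + 81×0.660 = 1202 mg, 54%;
- former 100 mg, 150 mg column: 1722 + 81×0.660 = 1776 mg, 79%.

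For assumed half-lives of 8 to 12 days, these become 142% to 117% against 93% to 75% (former 200 mg), and 62% to 49% against 92% to 71% (former 100 mg).

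**4. Two checks on how large this is.**
- Against the participant's own former 200 mg steady state, 2848/2987 = 95% (106% to 87% for 8 to 12 days).
- For a short gap of five missed doses (six days of decay), the same formulas give former 200 mg adults 120% against 114%, and former 100 mg adults 63% against 76%. The difference in level is therefore small for former 200 mg adults after a short gap.

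**The case against.** Table 13 is a menu: it offers 150 mg for every Part A dose and orders no one to remain on 100 or 200 mg. Its first footnote sentence has lapsed by its own condition. The stay rows are still needed for earlier enrollees, and Section 7.5.1 keeps individual stopping rules for the 200 mg dose. All of this stands. It makes the fault one of unrestricted leftover options, but the appendix that sites are sent to still permits a dose that the main text does not.

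The Table 14 columns do not name the previous dose, so a site could choose the column for the dose being started. If the lead-in is read strictly, it matches the Synopsis and Table 7 and may be a deliberate choice. That is also fair. The 77%, 77% and 93% are compatible with columns built for the dose being started, but they rest on an assumed model and do not establish intent. Intended or not, no reason is given for loading from the old dose when the dose changes after a gap that leaves about 5% of the earlier drug.

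A reader might infer from 4200 against 2100 mg that the plan creates a serious overexposure. The documents do not support that: on the same model the level is close to what a former 200 mg adult already had in Part A. A reader might also infer that the dose-group summaries are compromised. They are not. SAP Section 5.3 groups participants by the dose actually assigned on Day 1, and no hypothesis is tested.

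**Conclusion.** The point holds as an inconsistency in current dosing instructions, minor to moderate in weight. For Part A adults entering under Amendment 4, Table 13 permits maintenance doses that the main text does not. The lead-in to Table 14, the Synopsis and Table 7 point to a loading column that gives 67%, or 133% to 200%, of the load listed for 150 mg. The text comparison and the dose totals need no assumption; the level estimates depend on the one-compartment model and a half-life near 10 days.

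Not affected: adults enrolled before Amendment 4 who keep their dose, former 150 mg adults, and reductions allowed under Sections 5.3 and 7.5. The number affected is not given and may be zero. The worst case needs a former 200 mg adult, 42 or more missed days, entry after 08 Feb 2024 and a move to 150 mg, and neither document shows that such a participant exists. The past tense in SAP Section 2.2.3 suggests that enrolment has closed, though it does not say so.

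**What to change.** - In Table 13, limit the rows for staying on 100 mg and on up to 200 mg to participants enrolled before Amendment 4. Apply the same limit to the 200 mg level in Table 7 and to Section 7.5.1.
- State that later Part A entrants start at 150 mg except for permitted reductions.
- Delete the first sentence of the Table 13 footnote.
- In Table 14, say in both the lead-in and the column heads that the column is chosen by the maintenance dose assigned in C5351005.
- Amend the matching sentence in the Synopsis and Table 7 so that the loading dose is set by the dose being started and the length of the gap. Changing Table 14 alone would leave those two places contradicting it.

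The cost is wording in the Synopsis, Tables 7, 13 and 14 and Section 7.5.1, with no new data and no change to the analyses. If enrolment has closed, the edits only correct the record and change no one's starting dose. An optional SAP listing of Part A dose against Day 1 dose for anyone enrolled under Amendment 4 would show whether the ambiguity reached a participant.
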